**Plasma Pharmacokinetic Parameters on Day 1 (Period 1 & Period 2) for FE segment:**

Parameter	Definition
$C_{max}$	Maximum concentration which is directly determined from the plasma concentration time profiles
$T_{max}$	Time to maximum concentration. If the same $C_{max}$ concentration occurs at different time points, $T_{max}$ is assigned to the first occurrence of $C_{max}$ .
$AUC_{0-t}$	Area under the drug concentration-time curve, from time zero to the last measurable concentration using the 'Linear Up and Log Down' method
$AUC_{0-inf}$	Area under the drug concentration-time curve, from time zero to infinity ( $\infty$ ) using the following formula $AUC_{0-\infty} = AUC_{0-t} + \frac{C_t}{\lambda_z}$ 
Where, <math>C_t</math> is the observed concentration at the time t (last time point with a measurable plasma concentration above the quantification limit) at which quantification was still possible, the calculation of <math>\lambda_z</math> or <math>k_{el}</math> is given below.

$AUC_{\%extrap}$	The percentage of the AUC that has been extrapolated beyond the last observed data point, using the following formula $AUC_{\%extrap} = \left( \frac{AUC_{\infty} - AUC_{0-t}}{AUC_{\infty}} \right) \times 100$
$\lambda_z$ or $k_{el}$	The apparent terminal elimination rate constant, will be estimated from a regression of $\ln(C)$ versus time over the terminal log-linear drug disposition portion of the concentration-time profiles.
$t_{1/2}$	Apparent terminal half-life, using the following formula $T_{1/2} = \frac{\ln(2)}{\lambda_z}$
$T_{lag}$	$T_{lag}$ signifies the delay between the time of dosing and time of appearance of concentration in the sampling compartment
$CL/F$	Apparent total plasma clearance, using the following formula $CL/F = \frac{D}{AUC_{0-\infty}}$ 
Where D = Administered dose; <math>AUC_{0-\infty} = AUC_{0-inf}</math>

$V_z/F$	Apparent terminal volume of distribution, using the following formula $V_z/F = \frac{CL/F}{\lambda_z} \text{ Or } \frac{Dose}{\lambda_z \times AUC_{inf}}$
Corrected M/P ratio for $C_{max}$	Corrected metabolite to parent ratio for $C_{max}$ is calculated using the following formula $(C_{max} \text{ metabolite}/C_{max} \text{ parent}) * (\text{Molecular Weight of parent drug}/\text{Molecular Weight of metabolite})$

Corrected M/P ratio for AUC 0-t	Corrected metabolite to parent ratio for AUC 0-t is calculated using the following formula (AUC 0-t metabolite/ AUC 0-t parent) *(Molecular Weight of parent drug/Molecular Weight of metabolite)
--	---

If the pre-dose concentration following first dose administration is  $\leq 5\%$  of the  $C_{max}$  value, the participant's data will be included in both pharmacokinetic and statistical analysis without any adjustment. If the pre-dose value is  $> 5\%$  of  $C_{max}$ , the subject will be dropped from both pharmacokinetic and statistical analysis.

Additional pharmacokinetic parameters may be determined where appropriate.

Corrected metabolite to parent ratio will be calculated for  $C_{max}$  and AUC0-t for steady state and non-steady state dosing profiles of HS segments (SAD & MAD).

Pharmacokinetic analysis will be carried out using actual doses and blood sampling times, where possible. If actual times are missing, nominal times may be used with sponsor approval.

Plasma concentrations of EP547 (and its metabolites if applicable) will be used as supplied by the bioanalytical laboratory. The units of concentration and resulting PK parameters, with amount or concentration in the unit, will be presented as they are received from the bioanalytical laboratory.

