### 3.5 Handling of Missing Data

For the classification of Treatment emergent adverse event (TEAE) and Concomitant medication, the following will be applied in the following order:

- a. If all dates/times (start and stop) missing, the event/medication will automatically be classified as a TEAE/Concomitant medication.
- b. For adverse events (AEs) with a missing start date/time, if the event end date/time is prior to first study drug administration, the event will not be classified as a TEAE.
- c. If only the AE start year/ medication end year is present and is the same or is after the first study drug administration year unit, the event/medication will be classified as a TEAE/Concomitant medication.
- d. If the AE start month and year/medication end month and year are present and are the same or after the first study drug administration month and year units, the event/medication will be classified as a TEAE/Concomitant medication.

For the PK analysis the following will be applied:

- a. For the concentration descriptive summaries, concentrations may be excluded if sampling time deviation is considered large to affect the profile at the discretion of the pharmacokineticist.
- b. Concentrations (plasma and skin) that are below limit of quantification (BLQ which is 10 ng/mL undiluted) prior to the first quantifiable value will be set equal to zero. Post dose BLQ concentrations will be set to missing.
- c. Where there are no results (NR), these will be set to missing.
- d. If more than 75% of values per nominal timepoint and treatment group are BLQ, then all descriptive statistics, except for nBLQ, will be denoted as not calculable (NC).
- e. For the calculation and graphical representation (semi-log and log-log plots) of geometric descriptive statistics, 0 values will be set to missing.
- f. For the purpose of calculating the non-compartmental PK parameters, plasma concentrations that are BLQ prior to the first quantifiable value will be set equal to zero. BLQ values after measurable concentrations will be set to missing.
- g. For the calculation of summary statistics of PK parameters, all NR and NC values in a data series will be set to missing.

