## 10. PHARMACOKINETICS

### 10.1 Plasma PK Analysis

All PK summary tables will be based on the PK Population for plasma concentration data. All analyses will be summarized as described in section 3.1 (PK - continuous descriptive analysis). All listings will be based on the PK Population.

The following pharmacokinetic parameters will, where possible, be determined from the plasma concentrations of EP547 (and its metabolites if applicable) by non-compartmental method using Phoenix WinNonlin software (Version 8.1 or higher):

**Plasma Pharmacokinetic Parameters at non-steady state on Day 1 following single dose administration for SAD (SD) and MAD segments:**

Parameter	Definition
$C_{max}$	Maximum concentration which is directly determined from the plasma concentration time profiles
$T_{max}$	Time to maximum concentration. If the same $C_{max}$ concentration occurs at different time points, $T_{max}$ is assigned to the first occurrence of $C_{max}$ .
$AUC_{0-t}$	Area under the drug concentration-time curve, from time zero to the last measurable concentration using the 'Linear Up and Log Down' method
$AUC_{0-24hr}$	Area under the drug concentration-time curve, from time zero (time of dosing) to 24 hours post-dose using the 'linear Up and Log Down' method
$AUC_{0-48hr}$	Area under the drug concentration-time curve, from time zero (time of dosing) to 48 hours post-dose using the 'linear Up and Log Down' method (only for SAD cohort)

AUC 0-inf	
Area under the drug concentration-time curve, from time zero to infinity (<math>\infty</math>) using the following formula
 $AUC_{0-\infty} = AUC_{0-t} + \frac{C'_t}{\lambda_z}$ 
Where, <math>C'_t</math> is the observed concentration at the time t (last time point with a measurable plasma concentration above the quantification limit) at which quantification was still possible, the calculation of <math>\lambda_z</math> or <math>k_{el}</math> is given below.

AUC %extrap	
The percentage of the AUC that has been extrapolated beyond the last observed data point, using the following formula
 $AUC_{\%extrap} = \left( \frac{AUC_{0-\infty} - AUC_{0-t}}{AUC_{0-\infty}} \right) * 100$
$\lambda_z$ or $k_{el}$	
The apparent terminal elimination rate constant, will be estimated from a regression of <math>\ln(C)</math> versus time over the terminal log-linear drug disposition portion of the concentration-time profiles.

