#### 10.1.1.3 Calculation of AUC

- The minimum requirement for the calculation of AUC will be the inclusion of at least 3 consecutive plasma concentrations above the lower limit of quantification (LLOQ), with at least one of these concentrations following  $C_{max}$ .
- All AUC values will be calculated using the 'linear up / log down' trapezoidal rule where the linear trapezoidal rule will be used for increasing concentrations and the log trapezoidal rule for decreasing concentrations.

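### The metabolite-to-parent AUC ratio has no common end time, so it can be distorted in either direction and can change with dose because of the assay limit

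*SAP*

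**What the plan says.** SAP 10.1 defines AUC0-t as the area "from time zero to the last measurable concentration using the 'Linear Up and Log Down' method". The plasma parameters are to be derived for EP547 and, if applicable, its metabolites, so each analyte has its own end point.

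SAP 3.5 gives one assay limit ("BLQ which is 10 ng/mL undiluted") and names no separate limit for the metabolite. For the noncompartmental analysis, "BLQ values after measurable concentrations will be set to missing". Each area therefore stops at that analyte's last measurable sample. SAP 10.1.1.3 requires "at least 3 consecutive plasma concentrations above the lower limit of quantification (LLOQ") before an AUC is calculated.

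The AUC ratio is metabolite AUC0-t over parent AUC0-t, multiplied by a molecular-weight factor ("parent) *(Molecular Weight of parent drug/Molecular Weight of metabolite"). The text after the food-effect parameter table in SAP 10.1 says "Corrected metabolite to parent ratio will be calculated for" Cmax and AUC0-t "for steady state and non-steady state dosing profiles of HS segments (SAD & MAD"). Nothing says what to do when the two last measurable times differ.

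The same section defines AUC0-24hr, AUC0-48hr and AUC0-tau but does not use them for this ratio.

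**The concern.** A ratio of exposures is interpretable when both areas cover the same time. Here they need not. The molecular-weight factor is a constant and cannot correct a difference in time span.

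The sampling plan (protocol 12.1) makes a mismatch large when it occurs. Single-dose sampling goes from 48 h straight to Day 8, nominally 168 h, a gap of 168 − 48 = 120 h. After the last MAD dose it goes from 24 h to Day 14, a gap of 168 − 24 = 144 h. If one analyte is still above 10 ng/mL at the late sample and the other is not, the whole gap enters one side of the ratio only. Healthy-subject single doses ran from 25 to 675 mg, a 27-fold range, so which analyte reaches the late sample can change between groups. A constant true ratio could then appear to vary with dose.

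The SAP matches windows in its other ratios. The AUC accumulation ratio uses AUC0-tau over AUC0-tau, and renal clearance pairs 0–48 h urine with plasma AUC0-48 (SAP 10.2).

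**Working it through.** The documents state no value for this ratio, so there is no figure to reproduce.

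**Direction, without kinetic assumptions.** Let t_m and t_p be the last measurable times of metabolite and parent, and w the earlier of the two. Define

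factor = [AUC_m(0–t_m) / AUC_p(0–t_p)] ÷ [AUC_m(0–w) / AUC_p(0–w)].

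- If t_m < t_p, this reduces to AUC_p(0–t_m) / AUC_p(0–t_p), which is below 1.
- If t_m > t_p, it reduces to AUC_m(0–t_m) / AUC_m(0–t_p), which is above 1.
- If t_m = t_p, it is 1.

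**Size, simple model.** Inputs from the documents: LLOQ 10 ng/mL (SAP 3.5), the SAD sampling times (protocol 12.1), the monkey half-life of 18 h and a volume of 0.8 L/kg (protocol 5.3). Assumptions: 70 kg, so V = 0.8 × 70 = 56 L; F = 1; instantaneous absorption; metabolite = f × parent at all times. Then C0 = dose/56 L and, for half-life h,

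factor = (1 − 2^(−t_m/h)) / (1 − 2^(−t_p/h)).

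Example, 25 mg, f = 10%, h = 18 h: C0 = 446 ng/mL. Parent at 48 h is about 70 ng/mL and at 168 h about 0.7, so t_p = 48 h. Metabolite at 36 h is 11.2 and at 48 h 7.0, so t_m = 36 h. Factor = 0.750/0.8425 = 0.89.

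| h, f | 25 mg | 75 mg | 225 mg | 450 mg | 675 mg |
|---|---|---|---|---|---|
| 18 h, 10% | 0.89 | 1.00 | 1.00 | 0.84 | 0.84 |
| 18 h, 3% | 0.245 | 0.89 | 1.00 | 0.84 | 0.84 |
| 18 h, 30% | 1.00 | 1.00 | 1.00 | 0.84 | 0.84 |
| 12 h, 10% | 0.80 | 0.93 | 1.00 | 1.00 | 1.00 |
| 24 h, 10% | 1.00 | 0.76 | 0.76 | 0.76 | 0.76 |

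The 0.245 comes from a metabolite measurable only to 6 h: 0.206/0.8425. With f below 1 and equal half-lives, this model cannot give a factor above 1.

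**Size, when the metabolite may outlast the parent.** Parent: one-compartment oral, half-life 18 h, V = 56 L, assumed F = 1 and ka = 1.5/h. Metabolite: formed from parent, assumed AUC0-inf ratio 0.02 to 3 (to 1 for MAD), assumed half-life 4, about 18, or 36 h. LLOQ 10 ng/mL for both, linear-up/log-down areas, and the SAP's BLQ and three-point rules. Selected single-dose factors, with t_m/t_p in hours:

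| Metabolite half-life, AUC0-inf ratio | 25 mg | 75 mg | 225 mg | 450 and 675 mg |
|---|---|---|---|---|
| 4 h, 0.05 | 0.71 (24/48) | 1.00 (48/48) | 1.00 (48/48) | 0.84 (48/168) |
| about 18 h, 1 | 1.00 (48/48) | 1.73 (168/48) | 1.73 (168/48) | 1.00 (168/168) |
| 36 h, 0.3 | 1.00 (48/48) | 2.44 (168/48) | 2.43 (168/48) | 1.00 (168/168) |

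The full single-dose grid has 3 half-lives × 6 ratios × 5 doses = 90 cells. Seven are not calculable, 49 show no mismatch, 18 are low and 16 are high; the range is 0.71 to 2.44. The counts reflect the chosen grid and are not probabilities.

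MAD at 25, 75 and 225 mg, seven daily doses superposed: every calculable Day 1 case gives 1.00, both analytes ending at 24 h. Day 7 gives 0.60 at 225 mg when the parent reaches 168 h and the metabolite only 24 h, and 2.40 to 3.34 when the metabolite reaches 168 h and the parent only 24 h. These values assume that the Day 14 and Day 21 samples belong to the Day 7 AUC0-t, which the SAP does not state. If that area stops at 24 h, one mismatch is left: 0.60 at 25 mg (metabolite to 12 h, parent to 24 h).

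**The case against.** A reader might infer that the ratio is biased low, because metabolites often circulate below the parent. The documents do not support this. They give no metabolite concentration, half-life or separate assay limit, and upward distortion arises as readily once the metabolite may outlast the parent. Nor do they show that the two areas will in fact stop at different times.

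The illustrated effects are also fragile. In the simple model 10 of 25 cells are 1.00. The 450 mg effect depends on the parent being 12.5 ng/mL at 168 h. At an assumed 90 kg (72 L) it is 9.7, below the limit, and the factor returns to 1.00. At a 16 h half-life both top doses are below the limit at 168 h.

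The stakes can be overstated too. The AUC ratio is not a listed endpoint in SAP 2.3. A Cmax ratio is planned beside it. Fixed-window areas are planned for both analytes, and parent and metabolite parameters share tables (SAP 18, Tables 14.2.2a and 14.2.2b), so a matched comparison can be made from planned output. No formal testing is planned, the dose-proportionality tables cover EP547 only, and no planned analysis relates the ratio to dose. A false reading of saturable or induced metabolism is possible but is not built into the plan.

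Finally, a matched window is not automatically closer to the AUC0-inf ratio. With a 36 h metabolite half-life and AUC0-inf ratio 1, at 25 to 225 mg the SAP's ratio is 1.03 times the AUC0-inf ratio, while matching at 48 h gives 0.42 times.

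All of this stands and limits the point. It leaves the missing end-time rule in place: at 450 and 675 mg in that same example the SAP's ratio moves to 0.86 times the AUC0-inf ratio, solely because the parent now reaches Day 8.

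**Conclusion.** The concern holds in limited form. As written, the AUC ratio can compare different time spans within a subject. Relative to a matched-time ratio it is low when the metabolite ends first and high when the parent ends first; that follows from the definition alone. It can also vary with dose because of the 10 ng/mL limit and the late sampling gaps.

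The size cannot be known from the documents. The illustrations run from no effect in many cells to about 0.25- to 2.4-fold for single dose, taking both models together, and 0.6- to 3.3-fold for MAD Day 7. They rest on the monkey half-life, an assumed body weight, assumed metabolite kinetics and one assay limit for both analytes. The Day 7 range also depends almost wholly on including the Day 14 and Day 21 samples. These are ranges, not predictions.

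A downward bias, or a mismatch in every subject, is not established. The consequence is confined to one descriptive, supplementary parameter, so this is a worthwhile tidy-up rather than a threat to the trial's conclusions.

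**What to change.** In SAP 10.1, define the metabolite-to-parent AUC ratio over one window for both analytes:

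- SAD: AUC0-48hr where both analytes are measurable throughout.
- MAD: AUC0-tau (or AUC0-24hr) on the same condition.
- Otherwise: partial areas for both analytes to the earlier of the two last measurable times. The fallback is needed because a metabolite that is BLQ before 48 h or tau has no observed area beyond that point, and the SAP gives no rule for filling it.

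List both last measurable times and the window used beside each ratio, and compare doses only where the window is the same. State whether the Day 14 and Day 21 samples enter the Day 7 AUC0-t. Leave the Cmax ratio as it is.

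The cost is a formula change and one extra partial-area derivation for some subjects; no samples are added. The downside is that the matched-window ratio is not the AUC0-inf ratio and should not be labelled as such.

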### 10.1.1 Criteria for the Calculation of an Apparent Terminal Elimination Half-Life and AUC

#### 10.1.1.1 Number of Data Points

- In order for regression analysis to be performed, at least 3 data points will be included in the regression analysis and not including  $C_{max}$ .

#### 10.1.1.2 Goodness of Fit

- If data permits, the default 'best fit' method by Phoenix WinNonlin will be used for the selection of slopes to determine ' $\lambda_z$ '. If data do not permit, then the slope selection will be done by visual inspection or by a manual method to determine  $\lambda_z$ .
- When assessing terminal elimination phases, the adjusted  $R^2$  value will be used as a measure of the goodness of fit of the data points to the determined line.
- Regression-based parameters ( $\lambda_z$ , AUC0-inf,  $t_{1/2}$ , CL/F or CL/Fss, and  $V_z/F$  or  $V_z/F_{ss}$ ) will only be calculated if the adjusted  $R^2$  value of the regression line is greater than or equal to 0.8 and AUC%extrap is  $<20\%$ . If regression-based parameters cannot be calculated, they will be set to "NC", defined as "not calculable" in the data listings and summary tables as appropriate.

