$t_{1/2}$	
Apparent terminal half-life, using the following formula
 $T_{1/2} = \frac{\ln(2)}{\lambda_z}$
CL/F	
Apparent total plasma clearance, using the following formula
 $CL/F = \frac{D}{AUC_{0-\infty}}$ 
Where D = Administered dose; <math>AUC_{0-\infty} = AUC_{0-inf}</math>

$V_z/F$	
Apparent terminal volume of distribution, using the following formula
 $V_z/F = \frac{CL/F}{\lambda_z} \text{ Or } \frac{Dose}{\lambda_z \times AUC_{inf}}$
Corrected M/P ratio for $C_{max}$	
Corrected metabolite to parent ratio for <math>C_{max}</math> is calculated using the following formulae
 
(<math>C_{max}</math> metabolite/<math>C_{max}</math> parent) *(Molecular Weight of parent drug/Molecular Weight of metabolite)

Corrected M/P ratio for AUC 0-t	
Corrected metabolite to parent ratio for AUC0-t is calculated using the following formulae
 
(AUC0-t metabolite/ AUC0-t parent) *(Molecular Weight of parent drug/Molecular Weight of metabolite)

**Plasma Pharmacokinetic Parameters at steady state on pre-defined days following multiple dose administration for the MAD-HS and MAD-CP segments (Day 1 and Day 7) and for the MAD-UP segment (Day 1, Day 2, Day 6, and Day 7)**

Parameter	Definition
C max	Maximum steady state concentration time over the dosing interval
C trough	The pre-dose trough concentration observed at the last planned timepoint prior to next dosing
T max	Time to reach maximum concentration over the dosing interval. If the same C max concentration occurs at different time points, T max is assigned to the first occurrence of C max .
AUC 0-t	Area under the drug concentration-time curve, from time zero to the last measurable concentration using the 'Linear Up and Log Down' method
AUC 0-τ	Area under the plasma concentration-time curve over a dosing interval using the 'Linear Up and Log Down' method
AUC 0-24hr	Area under the drug concentration-time curve, from time zero (time of dosing) to 24 hours post-dose using the 'linear Up and Log Down' method
AUC 0-48hr	Area under the drug concentration-time curve, from time zero (time of dosing) to 48 hours post-dose using the 'linear Up and Log Down' method

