λ z or k el	The apparent terminal elimination rate constant, will be estimated from a regression of ln(C) versus time over the terminal log-linear drug disposition portion of the concentration-time profiles.
t ½	Apparent terminal half-life, using the following formula $T_{1/2} = \frac{\ln(2)}{\lambda_z}$
CL/F ss	Apparent total plasma clearance, using the following formula $CL/F_{ss} = \text{Dose} / AUC_{0-\tau}$
V z /F ss	Apparent terminal volume of distribution, using the following formula $V_z/F_{ss} = (\text{Dose}) / (\lambda_z \cdot AUC_{0-\tau})$
R auc	Accumulation ratio based on AUC, calculated as AUC 0-τ at steady state divided by AUC 0-τ after a single day
R cmax	Accumulation ratio based on C max , calculated as C max at steady state divided by C max after a single day
Corrected M/P ratio for C max	Corrected metabolite to parent ratio for C max is calculated using the following formula

---

	$(C_{\max} \text{ metabolite}/C_{\max} \text{ parent}) * (\text{Molecular Weight of parent drug}/\text{Molecular Weight of metabolite})$
Corrected M/P ratio for $AUC_{0-t}$	
Corrected metabolite to parent ratio for <math>AUC_{0-t}</math> is calculated using the following formula
 $(AUC_{0-t} \text{ metabolite}/ AUC_{0-t} \text{ parent}) * (\text{Molecular Weight of parent drug}/\text{Molecular Weight of metabolite})$

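### The SAP sets steady-state clearance (CL/Fss) to not calculable on an R² and extrapolation test, but its own formula, Dose/AUC0-τ, uses neither quantity

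*SAP*

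**What the plan says.** SAP 10.1.1.2 (Goodness of Fit) lists λz, AUC0-inf, t½, CL/F or CL/Fss, and Vz/F or Vz/Fss as regression-based. They are calculated only if the adjusted R² "value of the regression line is greater than or equal to 0.8 and AUC% extrap is" below 20%. "If regression-based parameters cannot be calculated, they will be set to" NC, not calculable. SAP 3.5, item g, then removes those values: "For the calculation of summary statistics of PK parameters, all NR and NC values in a data series will be set to missing".

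The steady-state parameter table in SAP 10.1 defines CL/Fss as Dose/AUC0-τ, and AUC0-τ as: "Area under the plasma concentration-time curve over a dosing interval using the 'Linear Up and Log Down' method". AUC has its own data rule in SAP 10.1.1.3, with no R² or extrapolation condition: "The minimum requirement for the calculation of AUC will be the inclusion of at least 3 consecutive plasma concentrations" above the LLOQ, at least one of them after Cmax.

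AUC%extrap ("The percentage of the AUC that has been extrapolated beyond the last observed data point") is defined from AUC0-inf and AUC0-t in the Day 1 and food-effect tables. Neither it nor AUC0-inf appears in the steady-state table, or in the non-exhaustive MAD parameter list of protocol 15.5. The steady-state table is headed as applying "at steady state on pre-defined days following multiple dose administration for the MAD-HS and MAD-CP segments (Day 1 and Day 7"), with Days 1, 2, 6 and 7 for MAD-UP.

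**The concern.** A parameter is regression-based if its formula uses the terminal slope. Single-dose CL/F (Dose/AUC0-inf) and Vz/Fss (which has λz in its denominator) do use it, and they are not part of this point. CL/Fss does not. No section exempts it from the gate.

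As written, one table could show AUC0-τ for a subject and NC for the dose divided by that same number. CL/Fss would then have a smaller n than AUC0-τ, from a subset selected by half-life. Its geometric mean need not equal dose over the geometric mean of AUC0-τ.

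CL/F is a named MAD outcome under a secondary objective. At 3:1 allocation, a MAD dose level of 8 to 12 subjects has only 6 to 9 on EP547.

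**Working it through.** The plan gives no figure to reproduce. The defect follows from setting the definitions side by side; the arithmetic only shows when it would matter.

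**Is the interval observed?** Protocol 12.1 samples every MAD segment to 24 h after the Day 7 dose. In MAD-UP the Day 6 interval closes with the Day 7 predose sample, taken less than 30 min before dosing (protocol Appendix C).

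**Inputs**
- τ = 24 h; extrapolation limit 20% (SAP 10.1.1.2).
- LLOQ 10 ng/mL (SAP 3.5).
- MAD-HS doses 25, 75 and 225 mg (protocol addendum, section 5).
- V = 0.8 L/kg (protocol 5.3) × 70 kg (assumed) = 56 L.
- Assumed: one compartment, F = 1, R² criterion met, log-normal half-life.
- Human half-life is not given; protocol 5.3 gives about 18 h for monkeys.

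**Cut-off when the profile ends at 24 h.** The extrapolated share is exp(−24k), with k = ln2/t½. It is 6.2%, 18.9%, 25.0% and 39.7% at 6, 10, 12 and 18 h. It reaches 20% at t½ = 24 × ln2/ln5 = 10.34 h (10.12 h with first-order absorption and tmax 2 h).

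**Share of subjects keeping CL/Fss when the profile ends at 24 h.** This is Φ[ln(10.34/median)/σ], with σ = √ln(1+CV²) = 0.294 at 30% CV.

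| Median t½ (h) | 30% CV | 20% to 40% CV |
|---|---|---|
| 6 | 97% | 92–99.7% |
| 8 | 81% | 75–90% |
| 10 | 54% | 53–57% |
| 12 | 31% | 23–35% |
| 18 | 3% | 0.3–7.5% |

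At 30% CV, that is about 3.3, 1.8 and 0.2 of 6 subjects at 10, 12 and 18 h. This case always applies to MAD-UP Day 6. It applies to Day 7 if Day 14 and Day 21 samples are not used.

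**If quantifiable Day 14 and Day 21 samples are used.** At t½ = 18 h the Day 14 concentration (168 h after the last dose) is about (Dose/56 L) × 1.656 × 0.00155. Here 1.656 is the accumulation factor 1/(1−0.397) rounded, and 0.00155 = exp(−168k). That gives 1.1, 3.4 and 10.3 ng/mL at 25, 75 and 225 mg, against a limit of 10. Simulated retention (400,000 subjects per cell, 30% CV) is therefore dose-dependent: 12–15%, 30–32% and 53–54% at 18 h. At 36 h it is 87–90%, 96–98% and 99%. With 20% to 40% CV, the 18 h figures become 3–26%, 19–41% and 51–58%.

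**Are the discarded values sound?** With constant clearance and no dialysis (so MAD-HS and MAD-CP only), Dose/AUC0-24 over true clearance is 1/(1−exp(−168k)) on Day 7. That is 1.000, 1.002, 1.008 and 1.041 at 12, 18, 24 and 36 h. A simulated oral profile on the Day 7 sampling times, with linear-up/log-down areas, agreed to within 1% of the true value for 8 to 24 h. On Day 1 the ratio is 1/(1−exp(−24k)): 1.33, 1.66, 2.00 and 2.70. A Day 1 value is therefore not a steady-state clearance.

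**Does AUC0-τ itself lean on λz?** A closing sample 30 min early leaves (exp(−23.5k) − exp(−24k))/(1 − exp(−24k)) uncovered: 0.4%, 1.0%, 1.3% and 1.6% at 6, 12, 18 and 36 h.

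**The case against.** The strongest reply is about consequence. CL/Fss is a fixed dose divided by AUC0-τ, which is listed by subject, so anyone can regenerate a missing value. CL/Fss enters no inferential analysis, and protocol 7.3.5 sets no pre-defined PK criteria to adjust or stop dosing. All of this stands, and it keeps the point modest.

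Second, the retention figures run from 0.3% to 99.7% and rest on an unknown half-life and an unsettled reading. AUC0-t runs to the last measurable concentration, which may point to including Day 14 and Day 21, and then most long half-lives pass. It could also be said that AUC%extrap, being absent from the steady-state table, has no value to act on there. The figures are indeed only illustrative. But 10.1.1.2 names CL/Fss outright, 10.4.1 repeats the 20% criterion for plasma, and the R² condition would apply regardless. That the reading is unsettled is itself a gap in the SAP.

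Third, because actual times are used, completing AUC0-τ to 24 h can need a short extrapolation. That is true, but at 0.4% to 1.6% it supports a coverage rule, not a 20% gate. AUC0-τ is also subject to 10.1.1.3, so it is reported wherever that rule is met, not automatically for everyone.

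**Conclusion.** The concern holds. Classing CL/Fss as regression-based contradicts the SAP's own definition, and this needs no assumption to show. How many values would be lost is conditional: none if every profile passes, and most if profiles end at 24 h and half-life is well above 10.3 h. The size and direction of any bias depend on half-life, on the correlation between clearance and volume, and on use of the follow-up samples, so no bias figure is claimed. The information is recoverable from AUC0-τ. This is a rule worth correcting, at the low end of importance.

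**What to change.** 1. Remove CL/Fss from the gated list in SAP 10.1.1.2 and apply the minimum-data rule of 10.1.1.3. State that a 24 h sample inside the Appendix C window counts as covering the interval. Section 10.4.1 needs no change for this.
2. Report CL/Fss on Day 7. Report MAD-UP Day 6 labelled as a dialysis-day value and not assumed equal to Day 7, since protocol 10.5 places dialysis on Days 1, 4 and 6. Do not report it as steady-state clearance on Day 1, or on MAD-UP Day 2, which also has no 24 h sample.
3. State whether Day 14 and Day 21 samples enter the Day 7 λz, AUC0-t and AUC%extrap.

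Separate listing corrections, which add no weight to the point:
- Remove Day 7 AUC0-inf from the MAD dose-proportionality lists in SAP 3.3 and 10.4.3. It carries over earlier doses: 1.33, 1.66, 1.98 and 2.60 times the single-dose value at 12, 18, 24 and 36 h, from (1−exp(−168k))/(1−exp(−24k)). Keep Day 1. Because protocol 15.5 names AUC∞ for the power model, record the change in SAP section 15.
- Delete AUC0-48hr from the MAD steady-state table, since no MAD segment has a 48 h sample.

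The cost is SAP wording and one noncompartmental-analysis rule, with no new data. Any CL/Fss already produced would be recalculated from AUC0-τ.
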